### 7.4. Dosage Modification

See Section [7.2.1](#).

### 7.5. Preparation/Handling/Storage/Accountability

The investigator or his/her designee is responsible for confirming appropriate temperature conditions have been maintained during transit for all study treatments received and that any discrepancies are reported and resolved before use of the study treatment.

Only patients enrolled in the study may receive IP, and only authorized site staff may supply or administer study treatment. All study treatments should be stored in an environmentally controlled and monitored (manual or automated) area in accordance with the labeled storage conditions, with access limited to the investigator and authorized site staff.

All insulin products must be stored at the investigative site under refrigerated conditions (between 2°C and 8°C) in a locked and secure place. Insulin must not be frozen.

In-use insulins should be maintained at room temperature and refrigerated material should be warmed to near room temperature before injecting. In-use insulin must not be used after 28 days.

The investigator is responsible for study treatment accountability, reconciliation, and record maintenance (such as receipt, reconciliation, and final disposition records).

## 7.6. Treatment Compliance

The investigator or designee will assess patient compliance at each visit, based on a review of the patient's glycemic control using available glucose values and HbA1c results, adherence to the visit and treatment schedule, and completion of the study diary. Patients who are deemed noncompliant will receive additional diabetes education and training, as required, and the importance of compliance with the protocol will be reinforced. Patients who, in the opinion of the investigator, are deemed consistently noncompliant may be discontinued from IP or from the study. No specific study data will be collected for analysis of treatment compliance.

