## 7.8. Treatment after the End of the Study

LY900014 will not be made available to patients after conclusion of the study. Rapid-acting insulin analogs are available in all countries for use as prandial insulin.

After discontinuation of IP at the end of the treatment period or earlier, it is recommended that patients return to their pre-study basal and prandial insulin; however, the choice of insulin therapy should be made by the investigator in consultation with the patient or caregiver.

Investigators should provide patients with appropriate guidance for glucose monitoring and insulin dose adjustment throughout the follow-up period in order to maintain glycemic control.

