## 8. Discontinuation Criteria

### 8.1. Discontinuation from Study Treatment

In the event that a patient is discontinued from the study treatment, the investigator should encourage the patient to remain in the study for continued safety monitoring. If the patient decides to continue in the study without IP, no early termination procedures will be completed. Patients will continue study visits through the safety follow-up.

Lilly recognizes the importance of complete data collection. This study includes elements to minimize missing data. Randomized patients who are discontinued from IP before study completion are encouraged to remain in the study for continued monitoring. For patients who remain in the study after early discontinuation of IP, both efficacy (including HbA1c) and safety data will be collected at scheduled visits. The difference between stopping IP and discontinuing the study will be explained to patients as part of the informed consent, and patients will be encouraged to continue in the study even if they stop study drug. In addition, study site investigators will be trained on the importance of complete data collection, with additional re-education of sites and patients as necessary.

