#### 8.1.1. Permanent Discontinuation from Study Treatment

Possible reasons leading to permanent discontinuation of IP are:

- **Subject Decision**
  - The patient/or the patient's designee, for example, parents or legal guardian requests to discontinue IP.
- The investigator may decide that the patient should stop IP. If this decision is made because of an AE, SAE, or a clinically significant laboratory value, the study drug is discontinued for that patient and appropriate measures are to be taken. Lilly or its designee is to be alerted.
- The patient becomes pregnant.
- An investigator, study site personnel performing assessments, or patient is unblinded, the patient must discontinue IP.
- The patient, for any reason, requires treatment with another therapeutic regimen or therapeutic agent that has been demonstrated to be effective for treatment of the study indication with the exception of those described in Section 7.7. Discontinuation from IP should occur prior to introduction of the new agent.
- Frequent use of prohibited concomitant medication, see Section 7.7.
- Patient has not taken IP for more than 14 consecutive days.
- Patient discontinuation is recommended by the DMC.
- **Discontinuation due to a hepatic event or liver test abnormality.** Patients who are discontinued from the IP due to a hepatic event or liver test abnormality should have additional hepatic safety data collected via case report form (CRF).

Discontinuation of the IP for abnormal liver tests **should be** considered by the investigator when a patient meets 1 of the following conditions after consultation with the Lilly-designated medical monitor:

- ALT or AST  $>8\times$ ULN
- ALT or AST  $>5\times$ ULN for more than 2 weeks
- ALT or AST  $>3\times$ ULN and total bilirubin level (TBL)  $>2\times$ ULN or international normalized ratio  $>1.5$
- ALT or AST  $>3\times$ ULN with the appearance of fatigue, nausea, vomiting, right upper quadrant pain or tenderness, fever, rash, and/or eosinophilia ( $>5\%$ )
- alkaline phosphatase (ALP)  $>3\times$ ULN
- ALP  $>2.5\times$ ULN and TBL  $>2\times$ ULN
- ALP  $>2.5\times$ ULN with the appearance of fatigue, nausea, vomiting, right quadrant pain or tenderness, fever, rash, and/or eosinophilia ( $>5\%$ )

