## **8.2. Discontinuation from the Study**

Patients will be discontinued in the following circumstances:

- enrollment in any other clinical study involving an IP or enrollment in any other type of medical research judged not to be scientifically or medically compatible with this study
- participation in the study needs to be stopped for medical, safety, regulatory, or other reasons consistent with applicable laws, regulations, and good clinical practice

- investigator decision
  - the investigator decides that the patient should be discontinued from the study
  - if the patient, for any reason, requires treatment with another therapeutic agent that has been demonstrated to be effective for treatment of the study indication, discontinuation from the study occurs prior to introduction of the new agent
- patient decision
  - the patient or the patient's designee, for example, parents or legal guardian requests to be withdrawn from the study

Patients discontinuing from the study prematurely for any reason should complete ED and other safety follow-up per Section 2 (Schedule of Activities [Table ITSB.1.](#)), Section 9.2 (Adverse Events), and Section 9.4 (Safety) of this protocol.

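### Protocol 8.2, and to a lesser degree 7.6, take patients out of the study where stopping IP would do, losing Week 26 HbA1c values that the ITT analysis needs (cheap improvement, modest effect)

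*Protocol*

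**What the plan says.** - Protocol 8.1 sets the retention policy. Patients off IP are encouraged to stay, and for them "both efficacy (including HbA1c) and safety data will be collected at scheduled visits".
- Protocol 8.1.1 covers a patient who needs another effective therapy, apart from the uses that 7.7 allows: "Discontinuation from IP should occur prior to introduction of the new agent".
- Protocol 8.2 covers essentially the same event, under investigator decision and without the 7.7 exception: "discontinuation from the study occurs prior to introduction of the new agent". A separate item there is open-ended: "the investigator decides that the patient should be discontinued from the study".
- Protocol 7.8 covers IP stopped at the end of treatment or earlier: "it is recommended that patients return to their pre-study basal and prandial insulin".
- Protocol 7.6 judges compliance on "glycemic control using available glucose values and HbA1c results", together with visit and treatment adherence and diary completion. After re-education it allows this: "Patients who, in the opinion of the investigator, are deemed consistently noncompliant may be discontinued from IP or from the study".
- Protocol 7.7 limits a non-study rapid analog to 14 days in total during the study and does not say whether the limit ends once IP is stopped.
- SAP 5.11.1 imputes a missing Week 26 HbA1c in the ITT analysis from same-arm patients who stopped IP but have the Week 26 value. If those records are fewer than the missing ones, or the model fails to converge, it imputes baseline plus noise.

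**The concern.** The ITT estimand uses all data regardless of IP use, so its quality depends on patients who stop IP and still give a Week 26 HbA1c. Section 8.1 is written to obtain those values. Section 8.2, taken at its word, ends study participation at the moment an off-IP patient starts replacement insulin, which in type 1 diabetes is unavoidable. Section 7.6 permits the same loss for noncompliance and states no purpose that stopping IP alone would not serve.

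Two things follow. Avoidable missing values accumulate, and the count that decides between copy reference and return to baseline shifts toward the latter. Under return to baseline, a patient whose control worsened is imputed at baseline plus noise. If the new insulin is truly worse, this pulls the arms together and favors noninferiority.

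**Working it through.** **1. The plan's own figures.** Inputs from Protocol 10.1: SD 1.1, 240/240/120 completers, one-sided 0.025. Power = Φ(distance/SE − 1.96).
- Margin 0.4: SE = 1.1√(2/240) = 0.1004; power 97.8% (stated: above 95%).
- Margin 0.3: power 84.8% (stated: above 80%).
- LY900014+20: distance 0.40 − 0.07 = 0.33, SE = 1.1√(1/240 + 1/120) = 0.123; power 76.5% (stated: about 76%).
- Randomized: 240/0.85 → 283, 120/0.85 → 142; 283 + 283 + 142 = 708.

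All reproduce. Power is not the issue: keeping 10 more values per blinded arm (5 in the open-label arm) gives only 98.2%, 86.2% and 78.2%.

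**2. The count rule.** Planned loss is 283 − 240 = 43 per blinded arm. Suppose all 43 stop IP. With 22 missing and 21 retrieved, retrieved < missing and the fallback applies. Keep one more who attends Week 26 and it is 21 against 22, so the count no longer triggers it. The gap moves by 2 per patient, but only for a patient who would have supplied the value.

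**3. Size when the fallback is in use.** The documents give no removal rate, so everything here is assumed: true difference 0.40; Week 26 SD 1.1; 283 per arm; late control (about Week 20) with SD 1.0, mean change 0 (Humalog) or 0.40 (LY900014), correlation 0.85 with Week 26. In the high-end case a patient is withdrawn with probability p = 0.05 or 0.10 if late control is more than 1.0 point worse. HbA1c is taken to be the same on or off IP.
- Share above the threshold: 1 − Φ(1.0) = 0.159 (Humalog); 1 − Φ(0.6) = 0.274 (LY900014). Times 283p: 2.2 or 4.5 and 3.9 or 7.8 patients. The largest is 7.8/43 = 18% of planned dropouts.
- Their mean Week 26 change is μ + 0.85 × 1.1 × φ(z)/(1 − Φ(z)): 0.935 × 1.525 = 1.43 (Humalog); 0.40 + 0.935 × 1.215 = 1.54 (LY900014).
- Imputed at zero change, arm means fall at p = 0.10 by 0.0159 × 1.43 = 0.0226 and 0.0274 × 1.54 = 0.0421. The difference falls by 0.0195, to 0.381. At p = 0.05 it is 0.390.
- SE = 1.1√(2/283) = 0.0925. False claim ≈ Φ(shift/SE − 1.96) = 3.2% and 4.0%. Simulation, which adds the imputation variance, gives 3.1% and 3.7%.

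Simulated false-noninferiority rates (nominal 2.5%; Monte Carlo error about 0.1 point):

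| Fallback in use | p = 5% | p = 10% |
|---|---|---|
| Removal on glycemic control alone | 3.1% | 3.7% |
| Same, HbA1c off IP moves halfway back to baseline (true difference 0.395 / 0.390) | 2.7% | 2.9% |
| Removal driven by a trait correlated 0.5 with control | 2.8% | 3.0% |
| Removal unrelated to control (about 3 / 6 per arm) | 2.8% | 3.0% |
| LY900014+20, 142 vs 283, removal on control alone | 3.0% | 3.4% |

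The fourth row can be checked by hand: 6/283 × 0.40 = 0.0085, and Φ(0.0085/0.0925 − 1.96) = 3.1%.

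**4. Existing checks, in the 3.7% case.** The tipping-point analysis gives 2.9% at delta 0.4, 2.6% at 0.6 and 2.2% at 0.8. The LOCF ANCOVA gives 2.5% if it can use an early-discontinuation HbA1c that tracks late control. If half of the retained patients supply Week 26, 3.7% falls to 3.0%; if all do, to 2.5%.

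**The case against.** The case for leaving the text alone is reasonable. Section 7.6 is permissive and follows re-education; discretion over persistently noncompliant families is ordinary. Sections 8.1 and 7.8 show that off-IP patients are expected to continue on other insulin, so a sensible site could work out the intent of 8.2. Noncompliance includes missed visits, and patients removed for that are the least likely to attend Week 26; for them the count does not move and the fix recovers nothing. The primary comparison is double-blind, sites are trained on retention, the tipping-point analysis runs until the result overturns, and reasons for discontinuation are compared by arm. An HbA1c is also requested on leaving: "Patients discontinuing from the study prematurely for any reason should complete ED and other safety follow-up".

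Most of this stands, and it limits the size. It does not remove the conflict between 8.2 and 8.1.1, and none of these safeguards recovers a Week 26 value. The early-discontinuation HbA1c is drawn at departure and is not the ITT endpoint.

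A reader might infer three stronger things that the documents do not support:
- That 7.6 contradicts 8.1 or makes poor glucose a ground for removal by itself. It lists several criteria together and says only that such patients may be removed.
- That every withdrawn patient shifts the count by 2. Only those who would have attended Week 26 do.
- That 3.7% is the expected error rate. It needs removal on control alone, the fallback in use and a true difference at the margin. The model does not include the other dropouts who would decide whether the fallback applies.

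**Conclusion.** The concern holds as a wording conflict with a modest consequence. The firmer part is 8.2 against 8.1 and 8.1.1: one event, two outcomes, and the literal reading of 8.2 removes the retrieved dropouts on whom the ITT analysis relies. Section 7.6 is a second, smaller route.

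On the assumptions shown, with the fallback in use and the true difference at the margin, the false-noninferiority rate is about 2.7–3.0%, with 3.7% at the high end. The real size cannot be derived because no removal rate is given. No inflation is claimed when copy reference is used. The efficacy-estimand MMRM does not use data after permanent IP discontinuation, so keeping the patient in the study makes no difference to it. Imputing a worsened patient at baseline is a property of the fallback for any missing patient; 8.2 and 7.6 only add avoidable ones.

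**What to change.** 1. Protocol 8.2: reword the item on another therapeutic agent so that IP is stopped before the new agent starts, as in 8.1.1, and the patient continues in the study under 8.1.
2. Protocol 7.6: delete the option of withdrawal from the study, so that consistent noncompliance can lead only to stopping IP.
3. Protocol 8.2: state that withdrawal by investigator decision is not to be used for noncompliance or poor glycemic control alone.
4. Protocol 7.7: state that the 14-day limit on a non-study rapid analog does not apply after permanent IP discontinuation. Otherwise a retained patient on replacement insulin would exceed it.

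Withdrawal for medical or safety reasons, or by the patient or family, is unchanged.

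The cost is one reworded item, one deleted phrase, two added sentences and a line in site training. Sites will follow some poorly adherent patients to Week 26, and some of those will still give no value, so recovery is partial.

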## 7.7. Concomitant Therapy

All concomitant therapies that are part of routine care are allowed and can be used during the study. Those listed in the exclusion criteria cannot be used. The subject should be encouraged to report any new concomitant medications after initiating the medication. Please check with the study team if you have any concerns or questions about a medication the subject is taking. Prohibited and restricted concomitant medications are listed below.

The following concomitant medications are NOT allowed at any time during the study

- Insulin glargine U-300, insulin degludec U-200,
- Afrezza® (inhaled insulin)
- premixed human or analog insulin
- Any noninsulin diabetes treatment therapy

The following concomitant medications ARE allowed for up to a total of 14 days during the study

- Regular human insulin, NPH or a nonstudy rapid analog insulin
- Systemic glucocorticosteroid
  - Including; intravenous, intramuscular, SC, or oral

## 7.8. Treatment after the End of the Study

LY900014 will not be made available to patients after conclusion of the study. Rapid-acting insulin analogs are available in all countries for use as prandial insulin.

After discontinuation of IP at the end of the treatment period or earlier, it is recommended that patients return to their pre-study basal and prandial insulin; however, the choice of insulin therapy should be made by the investigator in consultation with the patient or caregiver.

Investigators should provide patients with appropriate guidance for glucose monitoring and insulin dose adjustment throughout the follow-up period in order to maintain glycemic control.

## 8. Discontinuation Criteria

### 8.1. Discontinuation from Study Treatment

In the event that a patient is discontinued from the study treatment, the investigator should encourage the patient to remain in the study for continued safety monitoring. If the patient decides to continue in the study without IP, no early termination procedures will be completed. Patients will continue study visits through the safety follow-up.

Lilly recognizes the importance of complete data collection. This study includes elements to minimize missing data. Randomized patients who are discontinued from IP before study completion are encouraged to remain in the study for continued monitoring. For patients who remain in the study after early discontinuation of IP, both efficacy (including HbA1c) and safety data will be collected at scheduled visits. The difference between stopping IP and discontinuing the study will be explained to patients as part of the informed consent, and patients will be encouraged to continue in the study even if they stop study drug. In addition, study site investigators will be trained on the importance of complete data collection, with additional re-education of sites and patients as necessary.

#### 8.1.1. Permanent Discontinuation from Study Treatment

Possible reasons leading to permanent discontinuation of IP are:

- **Subject Decision**
  - The patient/or the patient's designee, for example, parents or legal guardian requests to discontinue IP.
- The investigator may decide that the patient should stop IP. If this decision is made because of an AE, SAE, or a clinically significant laboratory value, the study drug is discontinued for that patient and appropriate measures are to be taken. Lilly or its designee is to be alerted.
- The patient becomes pregnant.
- An investigator, study site personnel performing assessments, or patient is unblinded, the patient must discontinue IP.
- The patient, for any reason, requires treatment with another therapeutic regimen or therapeutic agent that has been demonstrated to be effective for treatment of the study indication with the exception of those described in Section 7.7. Discontinuation from IP should occur prior to introduction of the new agent.
- Frequent use of prohibited concomitant medication, see Section 7.7.
- Patient has not taken IP for more than 14 consecutive days.
- Patient discontinuation is recommended by the DMC.
- **Discontinuation due to a hepatic event or liver test abnormality.** Patients who are discontinued from the IP due to a hepatic event or liver test abnormality should have additional hepatic safety data collected via case report form (CRF).

Discontinuation of the IP for abnormal liver tests **should be** considered by the investigator when a patient meets 1 of the following conditions after consultation with the Lilly-designated medical monitor:

- ALT or AST  $>8\times$ ULN
- ALT or AST  $>5\times$ ULN for more than 2 weeks
- ALT or AST  $>3\times$ ULN and total bilirubin level (TBL)  $>2\times$ ULN or international normalized ratio  $>1.5$
- ALT or AST  $>3\times$ ULN with the appearance of fatigue, nausea, vomiting, right upper quadrant pain or tenderness, fever, rash, and/or eosinophilia ( $>5\%$ )
- alkaline phosphatase (ALP)  $>3\times$ ULN
- ALP  $>2.5\times$ ULN and TBL  $>2\times$ ULN
- ALP  $>2.5\times$ ULN with the appearance of fatigue, nausea, vomiting, right quadrant pain or tenderness, fever, rash, and/or eosinophilia ( $>5\%$ )

### **8.1.2. Temporary Discontinuation from Study Treatment**

Patients who temporarily discontinue the IP may have used non-study insulins. The patient will be allowed to resume IP if they have not taken IP for up to a total of 14 days on up to two occasions.

### **8.1.3. Discontinuation of Inadvertently Enrolled Patients**

If the sponsor or investigator identifies a patient who did not meet enrollment criteria and was inadvertently enrolled, then the patient should be discontinued from study treatment unless there are extenuating circumstances that make it medically necessary for the patient to continue on study treatment. If the investigator and the sponsor clinical research physician (CRP) agree that it is medically appropriate to continue, the investigator must obtain documented approval from the sponsor CRP to allow the inadvertently enrolled patient to continue in the study with or without treatment with IP. Safety follow-up is as outlined in Section 2 (Schedule of Activities Table ITSB.1), Section 9.2 (Adverse Events), and Section 9.4 (Safety) of the protocol.

## **8.2. Discontinuation from the Study**

Patients will be discontinued in the following circumstances:

- enrollment in any other clinical study involving an IP or enrollment in any other type of medical research judged not to be scientifically or medically compatible with this study
- participation in the study needs to be stopped for medical, safety, regulatory, or other reasons consistent with applicable laws, regulations, and good clinical practice

- investigator decision
  - the investigator decides that the patient should be discontinued from the study
  - if the patient, for any reason, requires treatment with another therapeutic agent that has been demonstrated to be effective for treatment of the study indication, discontinuation from the study occurs prior to introduction of the new agent
- patient decision
  - the patient or the patient's designee, for example, parents or legal guardian requests to be withdrawn from the study

Patients discontinuing from the study prematurely for any reason should complete ED and other safety follow-up per Section 2 (Schedule of Activities [Table ITSB.1.](#)), Section 9.2 (Adverse Events), and Section 9.4 (Safety) of this protocol.

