- For the 7-point self-monitored blood glucose (SMBG) profiles, the profiles measured after the first IP dose date and prior to the last IP dose date will be considered as data on IP.

Unless otherwise noted, all tests of treatment effects will be conducted at a 2-sided alpha level of 0.05, and confidence interval (CI) will be calculated at 95%, 2-sided. All tests of interactions between treatment groups and other factors will be conducted at a 2-sided alpha level of 0.05. Countries in similar geographic regions with fewer than 10 patients, based on all Randomized Population, will be pooled to achieve a pooled country of at least 10 patients. All analyses using country in the model will use a pooled country, unless otherwise specified. The final pooling by country and geographic region will be finalized prior to data lock.

[Table ITSB.5.2](#) shows the definition of baseline and post-baseline for each variable to be analyzed. The baseline variables are derived from the evaluable data during the baseline period.

Table ITSB.5.2. Baseline and Postbaseline Definitions and Patient Population by Study Period and Type of Analysis

Study Period/Analysis	Patient Population	Baseline Observations	Post-Baseline Observations
Lead-In Period			
HbA1c ANCOVA	All Randomized Patients	Visit 1	Visit 4 prior to initiation of IP
Basal, bolus, and total insulin doses, and bolus/total insulin dose ratios continuous analysis	All Randomized Patients	Not applicable	Visit 3-4
TEAE	All Enrolled Patients	Prior to first dose of open-label insulin lispro (or Visit 2 date if the dose date is missing)	The entire lead-in period after first dose of open-label insulin lispro and prior to the first dose of IP (or Visit 4 if the dose date is missing)
26-Week Treatment Period (including Safety Follow-Up Visit where applicable)			
HbA1c ANCOVA (ITT estimand)	All Randomized Patients	Last of Visits 1-4	Visit 15 with imputation for patients who discontinue study prior to Visit 15
HbA1c MMRM (efficacy estimand)	All Randomized Patients with a baseline and at least one post-baseline observation while on IP	Last of Visits 1-4	Visits 7, 10, and 15 prior to discontinuation of IP
HbA1c categorical analysis longitudinal logistic regression	All Randomized Patients with a baseline and at least one post-baseline observation while on IP	Last of Visits 1-4	Visits 7, 10, and 15 prior to discontinuation of IP

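### Protocol 8.1.1 stops only IP, while 8.2 ends study participation, for essentially the same trigger; where 8.2 is followed, a Week 26 HbA1c that 8.1 planned to collect goes missing from the FDA (ITT) analysis, in unknown numbers

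*Protocol*

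**What the plan says.** Protocol 8.1.1 lists reasons for permanently stopping IP. One is that the patient needs another regimen or agent with proven effect in the study indication. The item is qualified "with the exception of those described in Section 7.7" and ends: "Discontinuation from IP should occur prior to introduction of the new agent".

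Protocol 8.2 lists circumstances in which patients leave the study. Under the investigator-decision item, a second sub-bullet covers a patient who needs another agent shown to be "effective for treatment of the study indication, discontinuation from the study occurs prior to introduction of the new agent". It has no Section 7.7 exception and does not refer to 8.1.1.

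Four other protocol sections bear on this:

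- **8.1** encourages patients who stop IP to stay in the study. For those who do, "both efficacy (including HbA1c) and safety data will be collected at scheduled visits".
- **7.7** permits "Regular human insulin, NPH or a nonstudy rapid analog insulin" for up to 14 days in total.
- **8.1.2**, on interruptions, notes: "Patients who temporarily discontinue the IP may have used non-study insulins".
- **7.8** deals with stopping IP: "at the end of the treatment period or earlier, it is recommended that patients return to their pre-study basal and prandial insulin".

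For the FDA (ITT) analysis, SAP Table ITSB.5.2 defines the post-baseline observation as "Visit 15 with imputation for patients who discontinue study prior to Visit 15". Protocol 10.3.3.1 and SAP 5.11.1 impute from same-arm patients who stopped IP but have a Week 26 value. They switch to return-to-baseline imputation if that reference group has fewer records than there are missing values, or if the model does not converge.

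**The concern.** Two sections give a site opposite instructions for nearly the same event. One keeps the patient under observation off IP; the other removes the patient from the study.

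The event need not be rare. A patient with type 1 diabetes who stops the prandial study insulin will ordinarily need another prandial insulin, and 7.8 recommends a return to pre-study insulin. For patients who entered on aspart or glulisine (inclusion criterion 4), that insulin is a different agent. For those who entered on lispro, the point is arguable.

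At stake is the completeness of the primary endpoint under the ITT estimand, which is meant to use all data regardless of IP use. The gated tests follow the same ITT approach (Protocol 10.3.3.2, SAP 5.11.4), so they are exposed in the same way.

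**Working it through.** **1. The two rules side by side**

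| | Protocol 8.1.1 | Protocol 8.2 |
|---|---|---|
| Trigger | Another effective regimen or agent needed, whatever the reason | Another effective agent needed, whatever the reason |
| Exception | Section 7.7 therapies | None |
| Consequence | IP stops; 8.1 encourages the patient to stay | Study participation ends |
| HbA1c afterwards | Scheduled visits, including Visit 15 (8.1) | One sample at the early-discontinuation visit |
| Which rule governs | Not stated | Not stated |

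The triggers differ only in that 8.1.1 adds regimens and carries the exception. A switch to another effective agent outside 7.7 meets both.

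**2. What happens to the endpoint**

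A patient withdrawn under 8.2 before Visit 15 has an early-discontinuation HbA1c. The ITT row of Table ITSB.5.2 uses Visit 15, so the endpoint is imputed. Had the patient been retained, the Visit 15 value could have been observed and could have served as a retrieved-dropout record.

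**3. Effect on the imputation rule**

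For one arm, let K be the IP discontinuers who could be retained to Visit 15, M0 the values missing under any wording, and s the number of the K withdrawn under 8.2. The reference group has K − s records and the missing group has M0 + s. The count rule allows copy reference only if

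K − s ≥ M0 + s, that is, s ≤ (K − M0)/2.

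Each withdrawal narrows the gap by two records.

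**4. The plan's own figures**

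Protocol 10.1 reproduces. Randomized numbers are 240/0.85 = 282.4, rounded up to 283, and 120/0.85 = 141.2, rounded up to 142; 283 + 283 + 142 = 708. With SD 1.1, power is 97.8% for margin 0.4 (stated as above 95%), 84.8% for margin 0.3 (above 80%) and 76.5% for the open-label comparison (about 76%). The wording conflict makes none of these figures wrong.

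Planned non-completers are 283 − 240 = 43 per blinded arm and 142 − 120 = 22 in the open-label arm. The documents do not split them by cause.

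**5. Illustration of the count rule (assumed splits, not estimates)**

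| Arm | K | M0 | (K − M0)/2 | Fallback once s reaches |
|---|---|---|---|---|
| Blinded | 43 | 0 | 21.5 | 22 |
| Blinded | 33 | 10 | 11.5 | 12 |
| Blinded | 22 | 21 | 0.5 | 1 |
| Blinded | 21 | 22 | below 0 | Fallback whatever 8.2 says |
| Open-label | 22 | 0 | 11 | 12 |
| Open-label | 16 | 6 | 5 | 6 |
| Open-label | 10 | 12 | below 0 | Fallback whatever 8.2 says |

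Depending on the split, 8.2 could be decisive or irrelevant to the choice of method.

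**6. Direction of any effect (illustration)**

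Return-to-baseline imputation gives the imputed patients an expected between-arm difference of zero. Suppose a share m is imputed equally in both arms and a fraction p of the on-IP difference d persists off IP. The overall ITT difference is d[(1 − m) + mp]. The expected estimate after imputation is (1 − m)d. Fix the overall difference at the margin, 0.40, and take m = 0.15 purely as an example:

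- p = 1: d = 0.40, estimate 0.85 × 0.40 = 0.340.
- p = 0.5: d = 0.40/0.925 = 0.432, estimate 0.85 × 0.432 = 0.368.
- p = 0: d = 0.40/0.85 = 0.471, estimate 0.85 × 0.471 = 0.400.

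If the same patients are retained and observed, the expected estimate is 0.40 in every case. The shift therefore runs from none to 0.06 in favour of LY900014 as p goes from 0 to 1, and imputation noise works the other way by widening the interval. The documents give neither m nor p. Protocol 5.4 ties the endpoint HbA1c to about the last 3 months, so little should persist after an early switch and more might after a late one.

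**The case against.** The best defence is context. Section 8.1 says that patients off IP keep attending visits and have HbA1c collected. That makes sense only if a routine move to another insulin does not end participation. The SAP agrees: 5.11.1 relies on retrieved dropouts, 5.12.1 summarizes days on study after IP, and 6.2 encourages unblinded patients who must stop IP to continue in the study. The 8.2 item sits under investigator decision, and 7.7 and 8.1.2 are specific permissions that 8.2 does not expressly revoke.

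This stands as evidence of intent, and a narrower meaning for 8.2 is likely. It does not remove the conflict. The discretionary sub-bullet in 8.2 is a separate one; the disputed sub-bullet is directive, falls under a lead-in saying patients will be discontinued, and states no narrower meaning.

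A reader might go further in three ways that the documents do not support:

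- **All off-IP follow-up is lost.** That would leave 8.1 almost empty, which cannot be what was meant, and how sites would apply 8.2 is unknown.
- **The loss is capped at the planned 15% dropout.** That figure is an undivided planning assumption. Protocol 10.1 attaches it to completing the study, while 5.2 speaks of completing 26 weeks of treatment. It can be exceeded, and part of it (withdrawn consent, loss to follow-up) is missing under any wording.
- **The false-noninferiority rate is inflated.** Any such rate describes return-to-baseline imputation under an assumed share and persistence. That method is a separate prespecified choice and may be triggered regardless of 8.2.

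**Conclusion.** The contradiction is real and should be fixed; confidence in the wording conflict is high. Each patient withdrawn under 8.2 before Visit 15 who would otherwise have been retained costs the ITT analysis one observed Week 26 value and one potential reference record. This makes the return-to-baseline fallback more likely.

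The documents allow no estimate of how many patients are affected, nor of the direction or size of any effect on the noninferiority conclusion. The numerical examples above rest on assumed splits, shares and persistence and are illustrations only.

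Two things limit the reach. The efficacy-estimand MMRM uses data before permanent IP discontinuation and is largely unaffected. The tipping-point analysis (Protocol 10.3.3.1.1, SAP 5.11.3) stresses the imputed values, including with delta equal to 0.4, but it cannot recover values that were never collected.

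**What to change.** Reconcile Protocol 8.2 with 8.1, 8.1.1 and 7.7, and check the result against 7.8 and 8.1.2. In the reconciled text, state that scheduled HbA1c collection through Visit 15 continues, as 8.1 already plans, for patients whose only reason is this overlapping trigger and who have neither withdrawn consent nor left under another 8.2 item. Patients removed for other-trial enrolment, for safety or regulatory reasons, or by a separate investigator decision are outside this change. No position is taken on when IP is stopped or which insulin is used.

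The cost is a short wording change with no new visits or procedures. Because 8.2 is a directive withdrawal rule, the change may need an amendment rather than a site letter alone. It does not guarantee that copy reference will run, since the arm still needs at least as many retrieved records as missing ones. It does keep observed off-IP values in the ITT analysis.
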